7. INTRODUCTION

7.1. Indication

EXPAREL® was developed to extend pain relief with a single-dose administration without the use of indwelling catheters and to decrease the requirement for supplemental opioid medications.

EXPAREL is indicated for single-dose infiltration in adults to produce postsurgical local analgesia and as an interscalene brachial plexus nerve block to produce postsurgical regional analgesia.

Effective postsurgical pain control is a critical element in subject recovery following surgery, as the majority of subjects may experience significant pain, particularly in the first few days. Improved postsurgical pain management contributes to better healing, faster subject mobilization, shortened hospital stays, and reduced healthcare costs ([American Society of Anesthesiologists Task Force on Pain Management 1995](#)).

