13.1. Instructions for Conducting Procedures and Measures

All PK, sensory/motor function assessments, and safety assessments conducted after baseline (predose) will be timed from the end of the block. End of block procedure is defined as the time of completion of study drug administration after combined sciatic (in popliteal fossa) and saphenous (in the adductor canal) nerve blocks.

At timepoints when multiple assessments coincide, assessments will be performed in the following sequence: pain intensity assessment, sensory assessments, motor assessment, blood draw for PK assessment as applicable.

The **start of surgery** is defined as the time of the first incision. The **end of surgery** is defined as the time recorded in the surgical record. **Postsurgical** is defined as after the end of surgery.

Postsurgical analgesia and collection of study data through the primary endpoint will take place under the supervision of study staff at the site.

Subjects will be provided an e-diary on the day of surgery and instructed on duties and responsibilities with the e-diary.

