13.8. Health Care Facility Discharge

- Subjects in Cohort 1 and Cohort 2 will be discharged after the completion of the 168 h and 96 h assessments, respectively.
- Record date and time of health care facility discharge.
- Re-instruct on duties and responsibilities with the e-diary and for breakthrough medications.

13.9. Postsurgical Assessments from Discharge through POD 14

- Record pain intensity scores (NRS) measured as “What was your worst pain in the last 24 hours?” and “What was your average pain in the last 24 hours?” once daily at 21:00 (± 3 h) from the day after discharge (daily continuation from POD 1 to POD 14).

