8.1.3. Exploratory Endpoints

- 1. Subject satisfaction as measured by International Pain Outcome (IPO) at 96 hours
- 2. AUC of "average" pain scores from POD1 through POD4 and POD1 through POD14
- 3. AUC of "worst" pain scores from POD1 through POD4 and POD1 through POD14
- 4. Current pain intensity scores post-surgery through 96 hours

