administration will be included in this calculation. Note (1) the NRS score in the window that is higher than the worst value to be carried forward, this "higher" value will not be overwritten. Instead, the worst value will be replaced by this "higher" value and continue carrying forward until the end of the window. (2) if the scheduled NRS score within the window is missing, it will be imputed with this worst value.

B. After the wWOCF imputation described above, if there are still missing NRS scores at scheduled time points, they will be imputed using the multiple imputation procedures using the Markov Chain Monte Carlo (MCMC) method (Schafer 1997). This imputation will be carried out within each treatment group using SAS PROC MI. Thirty imputations will be conducted. To minimize the effect of data skewness on the imputation result, the NRS score is log-transformed [y=log(x+0.5), where y is the transformed score, x is the raw NRS score, and constant 0.5 is added to avoid log(0)] prior to the imputation and back-transformed after the imputation. In order to achieve the stationary distribution and to avoid dependency within samples generated by MCMC method, the number of iterations for the burn-in period will be set to 2000 and the number of iterations between two consecutive samples will be set to 1000.

For the imputed NRS scores, the associated time will be assigned with the exact scheduled time, eg, 48.0 h.

To better simulate the observed NRS pain score, all imputed scores will be rounded to become a number between 0.0 and 10.0 with 1 decimal place.

- C. The AUC at various time intervals will be derived as described in Section 9.5.1 from the imputed NRS scores. For each subject, there will be 50 sets of AUC from the 50 imputed data sets.
- D. The endpoints derived in Step C will be analyzed as described in Section 9.5.1 for each imputed data set.
- E. Rubin's (1987) synthesizing procedure will be applied to synthesize analysis results from the 50 imputed data sets. SAS PROC MIANALYZE will be used for this analysis. The least squares mean (LSM) and standard error (SE) for each treatment group, and the LSM, SE, 95% CI and p-value for the between treatment difference in AUC will be computed from this analysis.

The SAS pseudo-code for multiple imputations and analysis is as follows.

** Step (b) uses MCMC method to create fully imputed data sets

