9.5.4. Exploratory Endpoints

Assessment of subject satisfaction with pain control using International Pain Outcome (IPO) at 96 hours will be summarized by treatment group.

Current pain intensity collected 0 to 96 hours post surgery will be summarized by treatment group and analyzed for between treatment difference using ANCOVA at each scheduled time point. See Section 9.5.1 for model specification. This analysis will use wWOCF-imputed pain intensity data set (see Section 9.2.2A).

"Average" and "worst" pain score over the last 24 hours will be summarized by treatment group daily from POD1 through POD14. They will also be analyzed each day using ANCOVA (see Section 9.5.1).

AUC of "average" and "worst" pain scores will be calculated for each subject from POD1 through POD4 and through POD14 using the ranctangular area method as follows.

$$AUC_{0-4} = \sum_{i=\text{POD1}}^{POD4} p_i \text{ and } AUC_{0-14} = \sum_{i=\text{POD1}}^{POD14} p_i$$

The ranctangular method is chosen because the pain score here is already a summary of the last 24 hours pain by the patient.

For patients with monotone missing, (ie, once missing, all the following days are missing), the last observation carried forward (LOCF) will be applied to impute the missing daily scores. For patients with intermittent missing, the missing daily scores are imputed as follows.

$$p_x = \left(p_y + p_z\right) \frac{x - y}{z - y},$$

where x is the day with missing pain score, y and z are the days with non-missing pain scores closest to but before and after Day x, respectively. As an example, suppose Day 2 and Day 3 are missing, but Day 1 and Day 4 are collected, Day 2 and Day 3 pain scores are imputed as follows.

$$p_2 = (p_1 + p_4) \frac{2-1}{4-1} = 1/3(p_1 + p_4), \ p_3 = (p_1 + p_4) \frac{3-1}{4-1} = 2/3(p_1 + p_4).$$

For subjects with missing score for the first a few days, the first observation will be carried backward for the missing daily scores. AUC of "average" and "worst" pain scores will be summarized by treatment group. The between group difference will be analyzed using ANCOVA similar to the sensitivity analysis for the primary efficacy endpoint (Section 9.5.1).

A listing of admission and discharge to the surgical facilitate and PACU, postsurgical and pain medications will be provided.

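### Carrying the last daily pain score forward to POD 14 probably overstates the exploratory POD1-14 AUC and leaves imputation out of its standard error; the treatment difference may be biased, in a direction the documents do not settle

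*SAP*

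**What the plan says.** SAP 8.1.3 lists, as exploratory endpoints, the AUC of average and of worst "pain scores from POD1 through POD4 and POD1 through POD14". SAP 9.5.4 computes each AUC as a plain sum of daily scores and gives its reason: "The ranctangular method is chosen because the pain score here is already a summary of the last 24 hours pain by the patient". Each day therefore has equal weight, whether observed or filled.

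The filling rule depends on the pattern of gaps. Where scores stop for good, "the last observation carried forward (LOCF) will be applied to impute the missing daily scores". Missing first days are filled backward from the first score, and interior gaps have their own formula. The between-group difference is then analysed by ANCOVA. Section 9.5.4 does not pool over imputations.

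Protocol 13.8 sets the end of the facility stay: "Subjects in Cohort 1 and Cohort 2 will be discharged after the completion of the 168 h and 96 h assessments, respectively". Daily scores are due at 21:00 (±3 h) from POD 1 to POD 14 (Protocol 12.1), so the later ones depend on a diary kept at home.

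The primary endpoint is handled differently. Under SAP 9.2.2 step B, scheduled scores still missing after the opioid-window step are not carried forward: "they will be imputed using the multiple imputation procedures using the Markov Chain Monte Carlo (MCMC) method". This is done within each treatment group, and the results are pooled by Rubin's rules.

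**The concern.** LOCF assumes that pain stays where it was on the last day scored. The protocol's own picture is different: subjects "may experience significant pain, particularly in the first few days" (Protocol 7.1). If pain falls over two weeks, every carried day is too high.

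Timing matters most for Cohort 2, which is half the trial. If surgery ends at noon, 96 h falls at noon on POD 4, six hours before that evening's diary window opens at 18:00. A subject who stops the diary on leaving then has POD 3 as the last score, and a subject who completes that evening has POD 4. Protocol 13.9 describes home collection as starting on the day after discharge, which leaves the discharge-evening score unclear. Ten or eleven of the 14 days in the sum could then be copies of one early score. If the arms still differ on that day, the copies repeat the difference.

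What is at stake is how an exploratory two-week summary is read. SAP 2 allows planned analyses to go into study reports, submissions or manuscripts.

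**Working it through.** **Plan's own figure.** None exists for this endpoint. The only stated power (at least 90%) is for the 0-96 h primary AUC with 40 per arm, difference 150 and SD 170. It is met: 150/(170 × √(2/40)) = 3.95, and 3.95 − 1.96 = 1.99, which gives about 97.6%. It says nothing about POD1-14.

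**Inputs.** From the documents: the LOCF rule, equal weight per day, discharge at 96 h (Cohort 2) and 168 h (Cohort 1), and about 60 subjects per cohort. Assumed, because the documents give no values: the daily pain course, the daily treatment difference δ(t) (bupivacaine HCl minus EXPAREL), and the fraction d who stop the diary. Stoppers are assumed to stop at discharge, so the last day scored, k, is 3 or 4 in Cohort 2 and 7 in Cohort 1.

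**Level.** Bias in an arm's mean AUC = d × Σ over t>k of [μ(k) − μ(t)]. Assume the control mean falls linearly from 6 to 1.5, a slope of 4.5/13 = 0.346 per day and a true AUC of 14 × 3.75 = 52.5.
- k = 4: 0.346 × (1+…+10) = 19.04 per stopper
- k = 3: 0.346 × (1+…+11) = 22.85 per stopper
- k = 7: 0.346 × (1+…+7) = 9.69 per stopper

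With the cohorts in equal halves and d = 10%, the level rises by 0.10 × (19.04 + 9.69)/2 = 1.44 (2.7%) to 0.10 × (22.85 + 9.69)/2 = 1.63 (3.1%). At d = 20% these double to 5.5% and 6.2%.

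**Difference, equal stopping.** Bias = d × Σ over t>k of [δ(k) − δ(t)]. Assume δ = 2, 1.5, 1, 0.5 on POD 1-4 and 0 afterwards, for a true difference of 5.0.
- k = 4: 10 × 0.5 = 5.0
- k = 3: 0.5 + 10 × 1 = 10.5
- k = 7: 0, so Cohort 1 adds nothing

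| Stopping d | Cohort 2 last score POD 4 | Cohort 2 last score POD 3 |
|---|---|---|
| 10% | 0.10 × 0.5 × 5.0 = 0.25 (5%) | 0.10 × 0.5 × 10.5 = 0.525 (10.5%) |
| 20% | 0.50 (10%) | 1.05 (21%) |

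**Where the bias vanishes or reverses.** In the last two cases all stoppers have POD 4 as the last score.
- Constant effect, equal stopping: δ(k) − δ(t) = 0 on every day, so there is no bias.
- Rebound, with δ = 3, 2, 0, −1, −0.5 and then 0 (true 3.5), d = 10%: 0.10 × (−0.5 − 9 × 1) = −0.95. LOCF gives 2.55, an understatement.
- Unequal stopping under the fading effect. Each control stopper adds 19.04 and each EXPAREL stopper 19.04 − 5.0 = 14.04. With 5% of control and 15% of EXPAREL stopping: 5.0 + 0.952 − 2.106 = 3.85. With 15% and 5%: 5.0 + 2.856 − 0.702 = 7.15.

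**Scale against noise.** With an assumed between-subject SD of 1.3 and day-to-day SD of 1.0, the AUC SD is √(14² × 1.3² + 14 × 1.0²) = 18.6. With 40 per arm the SE of the difference is 18.6 × √(2/40) = 4.15. The 10% row of the table is then 0.06 to 0.13 SE.

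**The case against.** The strongest reply is that little depends on this. The AUCs are exploratory and outside the testing hierarchy of SAP 9.5. They stand beside a POD1-4 AUC and day-by-day summaries and ANCOVAs from POD 1 to POD 14, so a reader can see when any difference ends. Section 9.5.4 gives the filling rules after the AUC formula and does not say that the daily analyses use filled values. All of this stands, and it sets the priority.

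It can also be said that early gaps should be rare. Data through the primary endpoint are collected under staff supervision (Protocol 13.1), subjects are re-instructed on the diary at discharge (13.8), and worst and average pain are recorded at early termination (10.3.3). This makes a last score on POD 1 or POD 2 unlikely. It does not cover a Cohort 2 subject who remains in the study and simply stops the diary after discharge. The only later scheduled contact, for a subject without a persisting deficit, is the POD 14 call.

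A reader might infer that the rule must inflate the treatment difference and so manufacture a benefit lasting to POD 14. The documents do not support that. Inflation with equal stopping needs an effect that is larger on the last day scored than on average later, and no effect by day and no missing-diary rate by arm is stated. Even the overstatement of level is not universal: a subject last scored at a low value before pain rebounds is understated.

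Section 9.5.4 models its ANCOVA on the sensitivity analysis in 9.5.1. The text of that analysis was not available for this review, so nothing is assumed about it.

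**Conclusion.** The concern holds in a limited form. LOCF to POD 14 probably overstates the level of the POD1-14 AUC, by roughly 3% at 10% stopping under the assumed linear fall. The ANCOVA standard error contains no allowance for the filled days. The treatment difference can be biased. If the effect fades after discharge and stopping is similar in both arms, it is inflated by 5% to 10.5% at 10% stopping and 10% to 21% at 20%, under the assumed differences. With a constant effect and equal stopping the bias is zero, and with a rebound or unequal stopping it can reverse.

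The conclusion on level rests on pain falling after the first few days, which the protocol indicates only in words. The percentages rest wholly on assumed courses and stopping rates, and at 10% equal stopping the shift is small against sampling error. The primary endpoint is not affected. This is a desirable improvement, not an essential one.

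**What to change.** In SAP 9.5.4, replace LOCF and first-observation-carried-backward for the daily average and worst scores by the within-arm multiple imputation of 9.2.2. Use the POD1 to POD14 scores as the variables, compute the AUC in each completed data set, and pool with PROC MIANALYZE. Keep LOCF as a sensitivity analysis. State whether interior gaps are imputed in the same step, and report the number of missing daily scores by arm and day.

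The existing code already handles 16 time points, so 14 daily variables should need little change. Settle the number of imputations when reusing it: step B of 9.2.2 says thirty, while later steps and the code use 50. The method assumes that stopping depends only on arm and observed scores. That is still an assumption, but it does not hold pain fixed after the last entry. The cost is a few lines of SAP text and a little more programming for an exploratory endpoint.

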	POD 7	168h	±3h	х	х		
	POD 6	144h	±3h	х			
	S OOJ	120h	±3h	Х	Х		
		96h	±3h	Х	Х		
		84h	±2h	Х	Х		
_	04)	72h	±2h	Х	Х		
tration	4 (POI	60h	±2h	х	х		
dminis	ve Day	48h	±1h	х	х		
Drug A	operati	30h	±1h	х	Х		
study]	o Post-	24h	±1h	х	Х		
Post-	tration t	12h	±30m	Х	Х		
	Adminis	8h	±30m	Х	Х		
	ly Drug .	2h	±30m	х	Х		
	y of Stud	1h	±15m	Х	Х		
	Da	45m	45m ±5m X		Х		
		30m ±5m		Х	х		
		15m	±5m		х		
		Up to 15 mins	before blocks	Х	Х		
		Time Window		Collect PK blood sample; Record date and time of blood sample	Assess and record sensory and motor function ^{b,c}		

Table 2: Pharmacokinetic and Pharmacodynamic Assessment Schedule (Cohort 1 bunionectomy subjects only)

Abbreviations: h=hour; m=minute; PK=pharmacokinetic

a. All timepoints are from end of block administration.

- Once offset of sensory and motor block are determined (in two consecutive evaluations), no subsequent assessments will be conducted. Sensory and motor are assessed independently م
- When subject is in surgery, no sensory or motor block assessments be conducted.

5. **DEFINITIONS**

Start and End of Block

See Sections 6.3.1 and 6.3.2 for onset and offset of sensory block and motor block, respectively.

Study Day

Study Day is calculated as the date of event minus the date of end of study drug administration plus one (1), if the date of event is on or after the date of end of study drug administration. If the date of event is before the end of study drug administration, study day is the date of event minus the date of study drug administration.

Time 0

For PK, PD, and safety evaluation, Time 0 is defined as the date and time of the end of the study drug administration. For NRS pain collection and opioid consumption, Time 0 is defined as the date and time of the end of the surgery.

Baseline

Baseline is defined as the last available measurement prior to start of study drug administration.

Surgical Type

It is expected this study will enroll patients for bunionectomy, 1st metatarsophalangeal fusion, specific forefoot surgeries, midfoot fusion, hindfoot fusion, and total ankle arthroplasty. Due to overwhelmingly large number of bunionectomy patients enrolled as of this date, patients will be subgrouped into bunionectomy and non-bunionectomy for the purpose of by-subgroup summaries.

Treatment-Emergent Adverse Events (TEAEs)

TEAEs are those with onset date and time on or after the start date and time of study drug administration.

Beginning of Surgery

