9.2. Handling Missing Values

9.2.1. Total Post-Surgical Opioid Consumption

For the calculation of the total postsurgical opioid consumption 0-96 hours, both opioid pain medication before hospital discharge and opioid pain medication in the daily diary after discharge will be included. If opioid is taken on the start of study drug administration day but time is missing, time will be imputed as end time of surgery plus (+1) 1 minute. If opioid is taken after the day of study drug administration and time is missing, it will be imputed as 00:00.

For the calculation of the total dose through 96 hours, if a subject's last follow-up time is 96-x hours, then the opioid that was taken between 96-2x hour to 96-x hour will be used to project the amount from the last follow-up time to 96 hours, where time of last follow-up will be defined as the latter of (1) the last NRS pain assessment, (2) the start time of the last opioid pain medication, (3) time of the subject completion of the 96-hour satisfaction questionnaire, and (4) time of last sensory and motor block assessment.

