 - \circ A minimum number of three data points in the terminal phase will be used in calculating λ_z with the line of regression starting post the late C_{max} data point (C_{max} will not be part of the regression slope) and including the last point above LLOQ value (Ct).
 - \circ An appropriate number of decimal places will be used for λ_z to enable the reported value of terminal half-life (t_{1/2}) to be calculated.

- Rules for excluding subjects from the terminal phase-related parameter calculation:
 - 1. Adjusted R-square <80%, or
 - 2. %extrapolated AUC >30% of AUC_{0- ∞}
- Apparent terminal half-life $(t_{1/2})$ will be calculated as $\ln(2)/\lambda_z$.
- The area under the plasma concentration-time curve from the time of dosing to the time of the last quantifiable concentration (AUC_{0-last}) will be calculated using the linear-up log down trapezoidal method.
- The area under the plasma concentration-time curve from the time of dosing (zero) to infinity (AUC_{0-∞}) will be calculated as the sum of AUC_{0-last} and residual area C_t/λ_z.
- Extrapolated area under the curve from time of last point above LLOQ (t_{last}) to infinity (AUC_{extr}), expressed as percentage of AUC_{0-∞} will be calculated as (Ct/ λz)/AUC_{0-∞}·100%.
- Apparent clearance CL/F will be estimated as Dose/AUC_{0-∞}, where Dose = 266 mg for subjects receiving EXPAREL, 44 mg (50 mg × 0.886 [salt to free base conversion]) for subjects receiving 50 mg 0.25% bupivacaine, and 87 mg for subjects receive 100 mg 0.25% bupivacaine.
- Apparent volume of distribution (V_d/F) will be estimated as (CL/F) λ_z .

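### SAP 9.5.4's rule for intermittent missing daily pain scores is not linear interpolation: gaps of two or more days get wrong values, some above 10, and the exploratory POD1-4 AUC is too low when one gap spans POD4 and POD5

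*SAP*

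**What the plan says.** SAP 8.1.3 lists, as exploratory endpoints, the AUC of the daily average and worst "pain scores from POD1 through POD4 and POD1 through POD14". SAP 9.5.4 computes each AUC as a plain sum of daily scores and gives three rules for missing days:

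- No score after a certain day (monotone missing): last observation carried forward.
- First days missing: first observation carried backward.
- Gaps with observed days on both sides: "For patients with intermittent missing, the missing daily scores are imputed as follows", namely `p_x = (p_y + p_z)(x − y)/(z − y)`, with y and z the nearest observed days before and after day x.

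The worked example begins "As an example, suppose Day 2 and Day 3 are missing, but Day 1 and Day 4 are collected" and gives `p_2 = 1/3(p_1 + p_4)` and `p_3 = 2/3(p_1 + p_4)`.

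Two other calculation rules are relevant to the lesser points:

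- **SAP 9.6.1, dose used for CL/F.** One dose is 44 mg, from 50 mg times "0.886 [salt to free base conversion]) for subjects receiving 50 mg 0.25% bupivacaine". The next is "87 mg for subjects receive 100 mg 0.25% bupivacaine".
- **SAP 9.2.1, opioid total.** When last follow-up is at 96 − x hours, "the opioid that was taken between 96-2x hour to 96-x hour will be used to project the amount" for the unobserved hours. SAP Section 5 adds: "For NRS pain collection and opioid consumption, Time 0 is defined as the date and time of the end of the surgery".

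**The concern.** The weight `(x − y)/(z − y)` is the linear-interpolation weight, but here it multiplies the sum of the two neighbouring scores. It should multiply their difference and be added to the earlier score. A rule that fills in between two observed days should return those scores at its ends. This one returns 0 at x = y and `p_y + p_z` at x = z, so it cannot reproduce even a constant score.

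A programmer following the SAP would code it as printed. Imputed days could then fall outside the 0-10 scale or show pain rising when it fell. The POD1-4 AUC would be biased whenever its upper limit cuts through a gap. That limit lies near a change of setting, because "Subjects in Cohort 1 and Cohort 2 will be discharged after the completion of the 168 h and 96 h assessments, respectively" (Protocol 13.8). For Cohort 2, diary entry moves from the facility to home at about POD4.

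**Working it through.** **Inputs.** The formula, worked example and AUC as a sum of daily scores are from SAP 9.5.4. The 0-10 scale is from Protocol 13.1.1.

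**1. The plan's own example.** With y = 1 and z = 4 the weights are (2 − 1)/3 = 1/3 and (3 − 1)/3 = 2/3. This reproduces the printed example exactly, so formula and example agree with each other.

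**2. Difference from linear interpolation.** Let w = (x − y)/(z − y).

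- SAP: `w(p_y + p_z)`
- Linear: `p_y + w(p_z − p_y)`
- SAP minus linear: `p_y(2w − 1)`

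This is negative in the first half of a gap and positive in the second half. It is zero only at w = 1/2 (a one-day gap, or the middle day of an odd-length gap) or when `p_y` = 0.

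**3. Two-day gap, daily values.**

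| Observed before, after | SAP | Linear |
|---|---|---|
| 6, 6 | 4, 8 | 6, 6 |
| 8, 8 | 5.33, 10.67 | 8, 8 |
| 5, 3 | 2.67, 5.33 | 4.33, 3.67 |

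In the last row, falling pain is imputed as rising pain.

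**4. Values above 10.** On the last missing day of a g-day gap, w = g/(g + 1). The imputed score exceeds 10 when `p_y + p_z` > 10(g + 1)/g. That is 15 for g = 2, 13.3 for g = 3 and 12.5 for g = 4.

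**5. Sum over a complete gap of m days.** The weights k/(m + 1), k = 1 to m, add to m/2. The SAP sum is `m(p_y + p_z)/2`. The linear sum is `m·p_y + (p_z − p_y)m/2`, which is the same. The POD1-14 AUC is therefore unchanged, and so is the POD1-4 AUC unless one gap contains both POD4 and POD5.

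**6. Gap containing POD4 and POD5.** Let j of the m missing days fall at or before POD4. The POD1-4 error is

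`p_y[j(j + 1)/(m + 1) − j] = −j(m − j)p_y/(m + 1)`,

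whatever `p_z` is.

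| Observed days | m | j | Error | With `p_y` = 6 | Share of 24 (every day 6) |
|---|---|---|---|---|---|
| POD3, POD6 | 2 | 1 | −p_y/3 | −2.0 | 8.3% |
| POD2, POD6 | 3 | 2 | −p_y/2 | −3.0 | 12.5% |
| POD1, POD6 | 4 | 3 | −0.6p_y | −3.6 | 15% |

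All gaps within POD1-14 with an observed day on each side were then enumerated, with integer scores from 0 to 10. Whole-gap sums always agreed. For gaps containing POD4 and POD5, the POD1-4 error was negative in all 2970 cases with `p_y` > 0 and zero in all 297 cases with `p_y` = 0.

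**7. Lesser point (i), CL/F dose.** 50 × 0.886 = 44.3, printed as 44. 100 × 0.886 = 88.6, printed as 87. Even 2 × 44 is 88, so rounding does not explain it. 87/88.6 − 1 = −1.8%, so CL/F in the bupivacaine arm is 1.8% low. For the admix arm the components are 266 and 44.3, which add to 310.3 mg. The text does not say outright that they are to be summed.

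**8. Lesser point (ii), opioid projection.** The look-back starts at 96 − 2x, which is negative when x > 48, that is, before Time 0. Assume constant use, a look-back truncated at 0 h, and the look-back amount added unscaled:

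| Last follow-up | Hours of use counted | Shortfall against 96 |
|---|---|---|
| 48 h or later | 96 | 0% |
| 36 h | 36 + 36 = 72 | 25% |
| 24 h | 24 + 24 = 48 | 50% |
| 12 h | 12 + 12 = 24 | 75% |

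**The case against.** The strongest reply concerns reach. The affected endpoints are exploratory and outside the testing hierarchy in SAP 9.5. Of the AUCs, only POD1-4 can be wrong, and only for one kind of gap. Cohort 1 is in the facility to 168 h, so the risk lies mainly in Cohort 2. The percentages above are for single hypothetical subjects. All of this stands. The shift in an arm's mean equals the share of its subjects with such gaps times their average error, and the documents do not give that share.

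A second reply is that the imputation text follows the AUC formula, so it may serve the AUC alone and the odd daily values may never be analysed. That is a fair reading. SAP 9.5.4 does not say whether imputed scores enter the daily ANCOVA. It refers to Section 9.5.1, part of which was not in the text available for review, so no effect on that analysis is claimed.

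A third is that the SAP never calls its rule linear interpolation. This does not rescue it: no sensible rule turns 6 and 6 into 4 and 8, or produces 10.67 on a 0-10 scale. SAP 9.2.2 bounds the imputed scores for the primary endpoint to 0-10; Section 9.5.4 sets no bound.

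A fourth is that a gap running past POD4 might count as monotone within the POD1-4 window and so be handled by carrying the last value forward. The SAP's definition of monotone requires every later day to be missing. A gap with POD6 observed is therefore intermittent.

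On the lesser points, summing the two admix components is the ordinary reading. The opioid shortfalls depend on the assumptions in step 8, since the SAP does not say that the projection is unscaled. Last follow-up before 48 h should be uncommon with a planned stay through 96 h.

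**Conclusion.** The rule is wrong as written, and the worked example confirms that it is not a misprint. Daily values are wrong in any gap of two or more days, apart from exact midpoints and cases with `p_y` = 0, and can exceed 10. The POD1-4 AUC is understated by `j(m − j)p_y/(m + 1)` when one bounded gap contains both POD4 and POD5. This takes linear interpolation as the benchmark and judges monotone missingness over POD1-14. The POD1-14 AUC and the primary endpoint are unaffected, and the effect on any treatment comparison cannot be sized from the documents.

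The 87 mg figure conflicts with the SAP's own conversion factor, with a 1.8% effect on a descriptive PK parameter in one arm. The uncovered case in the opioid projection touches the first secondary endpoint, but only for very early dropouts. It is missing detail that would rarely matter.

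The formula should be corrected because it gives impossible values and costs almost nothing to fix. It does not threaten the trial's main conclusion.

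**What to change.** - **SAP 9.5.4:** replace the formula with `p_x = p_y + (p_z − p_y)(x − y)/(z − y)`. Correct the example to `p_2 = (2p_1 + p_4)/3` and `p_3 = (p_1 + 2p_4)/3`. If it is not settled in Section 9.5.1, add whether imputed scores enter the daily ANCOVA.
- **SAP 9.6.1:** reconcile 87 mg with the 0.886 factor, which gives 88.6 mg. State that the admix-arm dose in the CL/F calculation is the sum of both components (266 + 44.3 = 310.3 mg).
- **SAP 9.2.1:** add a rule for x > 48 h, for example scaling the observed hourly rate to the unobserved hours, with that assumption stated.

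The cost is one formula and its example, one figure, one clarifying clause and one or two sentences. Data collection does not change. Made before programming, the correction avoids a later departure from the SAP that Section 9.1 would require the study report to justify.
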